5. Impact. Although the main goal of this pilot study is to prepare for a future RCT that will definitively answer pertinent questions about the usability of EBPIs relative to fidelity/competence to therapeutic elements and subsequently quality of care, the results from this pilot still have the potential to make an impact on implementation and intervention science. This study will be part of the larger Center mission to begin creating a Typology of EBPI Targets for future intervention modification and potentially novel psychosocial interventions. It will also serve to inform the Center mission of identifying best methodology for EBPI modification (Matrix of EBPI Modifications). Although our R34 is focused on BA, the principles and findings from this study have the potential to inform the modification of other EBPIs.

INNOVATION

The main innovation from this project will be the implementation of UCD methods to the modification of EBPIs. Although the field has been aware of the complexities involved in supporting the adoption, use, and fidelity to EBPIs in public sector settings, the field has yet to interrogate how EBPIs – as they are designed by scientists – interacts with frontline clinicians in real-world practice, and whether clinician-informed modifications will indeed impact adoption, use and fidelity to EBPI elements.

APPROACH

[figure not shown]
Team Expertise. This multidisciplinary team is comprised of experts in EBPIs ([name], [name]), and Communications ([name]). Drs. [name] (qualitative research) and [name] (UCD expert) will serve as our design/build incubator experts. Expertise in EBPIs is needed on the team to ensure that the integrity of therapeutic elements remain intact. [name] is an expert in PST-PC, of which BA is a core component. We anticipate, based on 15 years of working with clinicians in primary care medicine, that methods for addressing anxiety and trauma exposure will be a likely usability feature clinicians will identify. [name] is an expert in Cognitive Processing Therapy and Exposure Therapy. Communications expertise is needed for the development of intervention materials that are understandable and appealing to clinicians. Additionally, identification of key talking points that are appealing to clinicians and highlight the collaborative effort of the modification to PST requires expertise in communication methods. [name] is an expert in the use of communications methods, including social media formats for raising health awareness in underserved communities. An innovation in her field will be the use of these methods for raising clinician awareness and subsequent adoption of EBPI elements.

Problem-Solving Therapy for Primary Care. PST-PC consists of up to 10 weekly sessions, with 6 sessions considered an adequate dose.^{45,79-82} In the first session the clinician provides an overview of the therapy, helps the patient create a list of problems to work on, and then shows the consumer how to use the PST process. All problems, solutions and action plans are identified and developed by the consumer, making this a consumer-centered intervention. In this process, the consumer identifies a problem area (Step 1), picks and explores a specific problem (Step 2), sets goals for the week (Step 3), considers alternative methods for meeting goals (Step 4) and selects an action plan (Step 5). Between sessions, the consumer implements action plans (Step 6) and in the next session, evaluates the success of the plan (Step 7). The process is applied to another

problem, until consumers become competent in solving problems on their own (maximum 10 weeks). As patients learn to use this model on their own, clinicians switch to a supportive stance. We elected to modify BA, not only because of its presence in primary care medicine, but because is a core component of PST-PC, and clinicians trained in PST-PC show almost immediate drift from the protocol⁸³, which appears to be driven by clinician concerns about intervention fit and ability to complete the PST-PC protocol in the window of time they have with their client⁷ (see preliminary study below).

Preliminary Studies. [name] has been the lead PST-PC trainer for the UW AIMS Center (an implementation and training center for collaborative care) for 15 years. In uncovering the challenges in training and sustained use of PST-PC among clinicians, important usability problems with PST-PC have been highlighted, specifically: (1) too many steps in a typical session; (2) not enough time to “get to know” the patient/not enough time to get through the process of PST-PC in each session; (3) too tiring to deliver on days when clinicians see PST-PC patients back to back; (4) focusing on problems was not synergistic with clinic mandates to use strength-based interventions; (5) difficulty using PST-PC to address common problems, such as lack of motivation, affect regulation, profound pessimism, trauma exposure, and access to basic needs in the face of poverty (food, shelter, access to health care, safety); (6) insufficient support to know when adding other EBPI elements or eliminating PST-PC elements was appropriate or in violation of protocol; (7) over-insistence by PST-PC trainers to have clinicians structure sessions and use of forms; and (8) perception that PST-PC was developed for research settings.

Study Overview. To accomplish the aims of the study, this project will be broken down into 3 phases that are st

Phase (Aim 3; see Fig.2). For phases 1 and 2, we will identify 15 representative clinicians working in FQHCs partnering with the AIMS Center and in the WWAMI region Practice and Research Network (WPRN). For phase 3, we will work with the Wyoming Family Practice Center in Casper, WY, a community health center that provides integrated mental health care to over 25,000 patients yearly (40% are on Medicaid or Medicare; see letter of support) to identify 6 representative clinicians and 30 patient participants, ≥18 years old with a PHQ9 of 10-20. The study will be conducted over a 2.5 year period during Y02 through Y04. Steps 1 and 2 will be conducted in the first 9 months of the study and Step 3 in the last 15 months (See timeline).

Phase 1/Aim 1: Discovery (3 months). The purpose of this phase is to uncover usability problems clinicians experience when implementing BA. Drs. [name] and [name] will be responsible for data collection and synthesis in this phase. As is detailed in the **Methods Core**, discovery data collection involves the identification of end-user needs (PAR process), contextual evaluation (IS process), and user testing (UCD process).

Clinician End Users. We will work with 10 PST-PC clinicians and 5 PST-PC naïve clinicians identified through the AIMS Center and through the WPRN. Previously certified clinicians need not be currently using PST-PC. The inclusion of untrained clinicians and previously certified clinicians who have abandoned PST-PC (or modified it for their use) is important to ensure we have a breadth of perspectives from different end-user types. Including naïve clinicians allows us to evaluate first impressions of PST-PC usability.

Identification of user needs. We will conduct semi-structured interviews with the 10 clinicians who were certified in PST-PC previously, using Zoom.com technology. The interview will interrogate challenges they face in implementing PST-PC that are related to (1) workflow, (2) patients they see, (3) PST-PC processes, and (4) any other challenges they may face. Questions will be tied to the seven common problems with usability (see Background Part 3) and CFIR constructs related to Intervention and Individual Characteristics (see **Methods**

Core). We will also ask about modifications they have made to the intervention to accommodate those challenges, and if they are no longer using PST, why. This interview will also cover PAR driven questions about what they value about their work with their patients, what they feel is missing when using PST-PC, and suggestions for how it could be improved, given their clinical context and patient population. Each clinician participant will be reimbursed \$50.00 for their time.

Contextual evaluation. We will conduct two WPRN site visits. We will shadow a clinician over the course of his or her day and make further observations about the clinician's workflow, to gather more impressions about how PST-PC could be modified to fit into the clinicians' daily routine, and observations of clinic and environment. Observations will be guided by the Consolidated Framework for Implementation Research (CFIR; see **Methods Core**), and will include observations of inner and outer settings and how they potentially influence the use of PST-PC.

User-Testing. All 15 of our clinicians will participate in BA training; for previously trained clinicians, the training will serve as a refresher of BA principles, and for BA naïve clinicians, they will be introduced to basic and core elements of BA. After the training, we will conduct a focus group with the naïve clinicians to ask their general impressions of BA and any concerns or thoughts they have about materials, the language in the materials, and how they think BA may or may not influence their workflow. Each clinician will then participate in a "think-aloud" exercise where the clinician uses BA with Drs. [name] and [name], who will play standardized simulated cases typically used for BA training. However, unlike simulated case training, where trainers provide corrective feedback, they will be instructed to verbalize what they are experiencing and thinking while engaged in the role play. As an example, a clinician who is struggling with the BA form may give impressions about what it is like to have their attention split between the form and the patient. The training and think-aloud exercise will be conducted on-line through the UWAC data portal and Zoom (see **Methods Core**). Think-aloud interaction will be recorded using Zoom.

Data Synthesis and Confirmation of Findings. Recordings of interviews will be transcribed and entered into Atlas.ti, a qualitative data analysis and research software, to organize data for coding by multiple coders. A codebook will be created to describe data codes and meaning of codes. Interviews will be coded by the qualitative interviewer and [name]. Coding will be grounded in the CFIR constructs. As interviews are coded, the results will be reviewed by the coders to discuss findings, resolve discrepancies, and identify any new themes. The final product from this data synthesis will be an **as-is workflow diagram** that describes the usability challenges with BA. As-is workflow diagrams allow for a pictorial representation of BA and identifies where bottlenecks, duplication of effort, and potential burdens lie. We will share these diagrams with the clinicians we interviewed for confirmation of accuracy of their experience using BA. After the as-is diagrams are completed, we will then share them with the Community Practice Board (CPB) members (see **Admin Core**) for further information and confirmation. Confirmation and input from a larger number of representative clinicians may enhance the generalizability of our modification. Finally, data collected on the implementation challenges of BA through these sources will be given to the Methods Core directors for use in the development of the Typology of EBPI Targets.

Phase 2/Aim 2 Design and Build Phase (6 months). The next step in the process will be to create initial prototypes of modifications to BA, based on the findings in the *Discover* phase. The Methods Core designer, working in consultation with Drs. [name] and [name], will create 3-5 initial prototypes. The process, described in the **Methods Core**, involves the same clinicians who participated in the *Discover* phase and has them work with the designer to create initial prototypes. In this context, prototypes will include work flow diagrams and storyboards representing the modification, materials and manuals. These prototypes will then be shared in our remote prototyping portal for clinicians to interact with and give further feedback for additional modification. Although we are not anticipating technology-based solutions, some modifications may include the use of technology to support intervention usability. We will iteratively improve designs through usability testing (e.g., with 5 participants per design iteration). For example, if the *Discover* phase finds that the BA process needs to include no more than 3 steps, they following iterative design process using the remote prototyping portal would occur as follows:

1. The design team will create 3 different ways BA steps could be condensed. These different processes will be depicted in electronic story boards.
2. The story boards will be shown to the clinicians with accompanying intervention materials (manuals etc). During the presentation, clinicians will be asked for their assessment of perceived usability (easy

of learning, potential for use in clinic, perceived burden, acceptability) for each iteration. These assessments will be both quantitative (System Usability Scale) and qualitative (Think Aloud). Quantitative data will be recorded on UWAC data portal, as will audio recordings of the Think Aloud Assessment.

3. Designers will then create a new version of the modification using information from all three storyboard assessments. The next version will be assessed using the processes described in step 2. This will continue until we reach a SUS scale score of .80.

A final prototype will undergo initial feasibility evaluation in pilot field deployments with each clinician using the prototype with one patient. Once we have completed the redesign of BA so that it (1) meets needs of its clinicians and patients (i.e., is useful), and (2) is easy to use and understand (i.e., is usable), we will move to the *Test* phase of this study.

Phase 3/Aim 3: Test phase (15 months). We will conduct a pilot study comparing the modified version of BA to usual care. Therapists will be randomized to either modified BA, and will use their assigned intervention with 5 patients.

Patient eligibility. Patient participants will be identified through each clinic's electronic health record. Participants must be 18 years old or older, suffering from mild to moderate depression. The site champion will identify potential participants from their electronic health records (EHRs) who score between 10 and 20 on the PHQ-9 and will contact potentially eligible patients to conduct a preliminary screening for eligibility, provide a brief description of the study and obtain informed consent.

Clinician training in modified BA. [name] and [name] will train clinicians in the modified BA. We will follow the protocol developed by the AIMS Center, which includes training in basic brief treatment skills, therapeutic elements of the intervention and therapy process. This is followed by simulated case training.

Clinician data collection. Two types of data will be collected, clinician assessment of intervention usability, and clinician ability to learn the intervention and maintain competency. To measure **intervention usability**, clinicians will complete the ALFA-Q Acceptability Scale, the User Burden Scale and the System Usability Scale, which are core measures for this Center (see **Methods Core** for description of scales). **Learnability** of the interventions will be measured in number of role plays needed to reach competency during training. To measure **sustained competency**, clinicians will collect audio recordings of patient sessions for review by experts. Drs. [name] and [name] will conduct these reviews using each intervention's adherence scale. Sustained competency will be defined by (1) time to first session rated < 4 ("good") and (2) number of sessions rated < 4 ("good") once certified. Clinicians will not be given feedback on session performance.

Patient data collection. We will use the UWAC data portal, which will be based on the UWAC Data portal⁸⁴ designed specifically for research on mobile depression interventions to confirm eligibility, complete the consent process, and conduct baseline and outcomes assessment (see **Methods Core** for further details.) For qualitative interviews, we will use Zoom.com, a secure teleconferencing service with HIPAA-compliant data security features and the capacity to record sessions. Patients can participate either by phone or video. Participants will receive \$20 for completing each of 2 (baseline and post-treatment) assessments. Patient data will be collected before treatment initiation and after treatment ends. Patients will complete a demographic survey to determine gender, age, race/ethnicity, income categories, and educational level. Patients will complete a series of brief clinical measures to determine the presence of a depressive disorder and if there are any important comorbidities. The *Sheehan Disability Scale (SDS)*^{85,86} is a brief analog scale measuring functioning in work, social, and health domains, using visual-spatial, numeric and verbal anchors. The scale has been validated in medical and psychiatric populations with a variety of psychiatric diagnoses.^{85,86} The *9-item Patient Health Questionnaire*⁸⁷ (PHQ-9) consists of 9 DSM depression symptoms and one disability item. It has been found to have excellent sensitivity to change over time (sensitivity = .88, sensitivity = .80).⁸⁸

Data analysis. Aim 3 focuses on pilot feasibility data to inform a larger (future) clinical trial comparing modified BA to usual care. Thus, analyses do not focus on hypothesis-driven inferential statistics but rather on descriptive statistics, graphical summaries, and basic effect sizes. **H1: Usability.** Differences in clinician-reported usability

between modified BA and usual care will be plotted using a dotplot and tested using a *t*-test using the SUS and UBS as dependent variables. **H2: Fidelity/Competence:** A similar strategy (dotplot, *t*-test) will be used with number of hours to reach certification. Number of sessions with fidelity scores <4 (“good”) will be summarized as proportions, both by clinician and by treatment. Between-treatment differences will be tested with a 2-sample proportion test. (Future analyses with larger sample size will use a generalized linear mixed model approach to account for the nested data^{89,90}.) **H3: Patient Reported Outcomes.** Histograms and kernel density estimates will be plotted by treatment condition to explore differences on depression outcomes (PHQ-9 total score) and overall daily functioning (SDS). Descriptive statistics (*M* and *SD*) will also be examined by clinician and by treatment, using Cohen’s *d* as an effect size summary. A *t*-test will be used to examine treatment differences in patient outcomes. Of ultimate interest is whether the modified treatment has its impact on patient outcomes through enhanced usability and clinician fidelity. We will use graphical summaries of the data to explore the relationships that are consistent with mediation (e.g., correlation of usability with patient outcomes [b pathway], and treatment differences on patient outcomes with fidelity partialled out [c’ pathway]). The primary focus here is whether the data and relationships appear consistent with mediation, as opposed to a formal test, which will be dramatically under-powered.

Power and Sample Size. Sample sizes for Aims 1 and 2 were based on estimates from the UCD literature on necessary number of participants to capture critical design information, where the recommendation is 5-10 end users. As Aim 3 is focused on gathering information (feasibility, recruitment and retention rates, response and attrition rates, etc.) for a future R01 application, the sample size was set primarily for practical reasons and used estimated effect sizes, rather than being driven by hypothesis testing.

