Phase 1 & 2: We will recruit clinicians via informational letters about the study and talking points for phone scripts.

Phase 3: Clinician participants will be recruited based on past participation in the Design phase of this study. Some new clinician participants will also be recruited for Phase 3 based on recommendation of these past participants who completed the Design phase and work in the same clinic. Participants will be recruited by email.

Patient Participants: Patients will be identified through electronic health records with a PHQ-9 score between 10-20. Patients will only be contacted and recruited if they are chosen to complete exit interviews. For those identified for exit interviews, they will be approached by BVHC staff either in person or via email, the study will be briefly explained to them, and then they will be asked if they are willing to complete an exit interview. For those willing, their contact info will be provided to UW study staff to reach out for further explanation and consent.

Note that site champions will complete CITI Human Subjects Protection training and will be trained by study staff regarding appropriate procedures for recruitment. We will make it clear to site champions that the consequences of coercing patients into study participation will be removal from the study protocol.

- b. Upload descriptions of each type of material (or the materials themselves) to the **Consent Forms and Recruitment Materials** SmartForm of **Zipline**. If you will send letters to the subjects, the letter should include a statement about how you obtained the subject's name, contact information, and any other subject-specific information (such as a health condition) that is mentioned in the letter.

HSD encourages researchers to consider uploading descriptions of most recruitment and screening materials instead of the materials themselves. The goal is to provide the researchers with the flexibility to change some information on the materials without submitting a Modification for IRB approval of the changes. Examples:

- *You could provide a list of talking points that will be used for phone or in-person conversations instead of a script.*

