Aim 1: Discover Phase (3 months). Using iterative and participatory methods, we will interview 10 clinicians from FQHCs affiliated with the WWAMI region Practice Research Network (WPRN, a collaborative group of primary care practices through the states of Washington, Wyoming, Alaska, Montana and Idaho to facilitate innovative community-based research), and observe them using PST-PC to identify usability challenges.

[figure not shown]
Contribution to the Center: Data from this phase will be used to inform the Typology of EBPI Targets.

Aim 2: Design/Build Phase (6 months) After identification of potential targets, the research team will work with the original 10 clinicians to engage in a rapid cycle of iterative prototype development and testing (e.g., storyboarding, paper prototypes) of BA modifications. The build of these modifications will include the development of intervention prototypes for user testing and refinement with input from these care managers.

Contribution to the Center: Data from this phase will be used to inform the Matrix of EBPI Modifications.

Aim 3: Test Phase (15 months). We will test and compare the BA modification (Task Sharing) to usual care in a small non-randomized trial. We will assign all provider teams (therapist & care manager(s)) in the clinic to use Task Sharing with their patients. We will then compare patient outcomes for those receiving Task Sharing vs. patients receiving usual clinic care. H1: Modifications developed in the Design/Build phase for targets identified in the Discover Phase will result in better usability (System Usability and User Burden Scales) compared to usual care. H2: Task Sharing will be more effective than usual care on improving clinical outcomes of functional disability (Sheehan Disability Scale [SDS]), change in depression symptoms over time (PHQ-9 total score), and change in anxiety symptoms over time (GAD-7 total score).

This study directly addresses IOM report recommendation 3-1: conduct research on psychosocial intervention elements and NIMH SP 4.1 Improve efficiency and effectiveness of existing mental health services.

SIGNIFICANCE

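### The appended research plan contradicts itself and the application on the Phase 3 design: randomised therapists with 30 patients at Casper, or a non-randomised comparison of up to 40 + 40 patients at Bighorn Valley

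*Combined protocol and SAP*

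**What the plan says.** Two accounts of Phase 3 stand in current text.

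The first is in the appended research plan. Its Study Overview says "For phase 3, we will work with the Wyoming Family Practice Center in Casper, WY" and continues "to identify 6 representative clinicians and 30 patient participants". The Phase 3/Aim 3 text adds "Therapists will be randomized to either modified BA, and will use their assigned intervention with 5 patients". Under Patient eligibility, the site champion "will contact potentially eligible patients to conduct a preliminary screening for eligibility, provide a brief description of the study and obtain informed consent". Under Patient data collection, consent and the baseline and post-treatment assessments run through a data portal.

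The second is in the application and also in the research plan's own Specific Aims. Specific Aims, Aim 3, says "We will test and compare the BA modification (Task Sharing) to usual care in a small non-randomized trial" and "We will assign all provider teams (therapist & care manager(s)) in the clinic to use Task Sharing with their patients". Section 1.5 repeats the non-randomised design with 40 modified-BA patients (10 per provider team) and 40 usual-care patients. Section 5.1 places the study at Bighorn Valley Health Center (BVHC), with up to 40 patients in each group, 80 in total, and 11 clinicians. Section 4.2 says "Patients will only be contacted and recruited if they are chosen to complete exit interviews". Sections 5.1 and 8.2 take patient outcomes from the electronic health record (EHR) without consent.

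Section 3.1 still refers to clinics in both Wyoming and Montana. On size, the Power and Sample Size paragraph says only that "the sample size was set primarily for practical reasons and used estimated effect sizes".

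**The concern.** Allocation method, site, number of clinicians, number of patients and route of patient entry all differ between the two accounts, and no text says which one governs. The conflict is not confined to application versus appendix: Specific Aims and the Phase 3/Aim 3 text belong to the same research plan.

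The randomisation sentence comes shortly before the only statistical analysis text. That text promises Cohen's d and a t-test by treatment on patient outcomes without saying how patients come to be in each group. Someone reading the plan in order could report the result as a randomised contrast. If the non-randomised account is the true one, a difference between groups may reflect differences between clinics, providers or selected patients, and the future trial this pilot is meant to inform would inherit that misreading.

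**Working it through.** **Step 1: is each account consistent in itself?**
- Casper account: 6 clinicians (Study Overview) × 5 patients each (Phase 3/Aim 3) = 30, which matches the stated 30.
- BVHC account: 40 + 40 = 80 (1.5 and 5.1), which matches the stated 80. At 10 per team (1.5), 40 / 10 = 4 teams.

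Both reproduce, so neither figure is a slip that rounding or a typing error would explain.

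**Step 2: the accounts side by side.**

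| Element | Study Overview, Phase 3/Aim 3 and Patient data collection | Application and Specific Aims |
|---|---|---|
| Allocation | therapists randomised, second arm not named | non-randomised (1.5; Specific Aims) |
| Site | Casper, WY | BVHC (5.1) |
| Clinicians | 6 | 11 (5.1) |
| Patients per unit | 5 per therapist | 10 per team (1.5) |
| Patients | 30 | 40 + 40 (1.5); up to 40 per group, 80 in total (5.1) |
| Patient entry | contacted, screened and consented, then assessed through a portal | EHR data without consent; contact only for exit interviews (4.2, 5.1, 8.2) |

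No single section carries the whole BVHC account. Specific Aims gives only the non-randomised design, 1.5 adds the numbers, and 5.1 gives the site and clinician count. On allocation, site and numbers, these sections are compatible with one another and not with the Casper text.

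**Step 3: does the analysis text decide?** Data analysis and Power and Sample Size name no allocation method, no site and no Phase 3 number. They do not.

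**Step 4: size of the difference.** 80 − 30 = 50 patients, a ratio of 80 / 30 = 2.67, and 11 − 6 = 5 clinicians. The 30 is a target, whereas 5.1 words the 40s as maxima.

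**Step 5: illustrative precision.** With Cohen's d near 0 and independent patients, the 95% half-width is about 1.96 × √(1/n₁ + 1/n₂).
- 15 + 15 (an assumed equal split of 30): 1.96 × √(2/15) = 0.716.
- 40 + 40: 1.96 × √(2/40) = 0.438.
- Ratio: 0.716 / 0.438 = 1.63.

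Clustering by provider is ignored. The documents give neither an intraclass correlation nor the number of patients per usual-care provider.

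**The case against.** The best reply is that the intended design can be inferred. The randomisation sentence is visibly broken, with only one arm after its either. Specific Aims, 1.5 and 5.1 fit together and describe a BVHC comparison. This is a pilot whose analysis is mainly descriptive. Much of that stands: the Casper text is probably a remnant, and the precision argument carries little weight. But nothing labels it superseded, section 3.1 still names Wyoming, and a plan should not leave its allocation method to inference.

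Three stronger readings are tempting, and the documents do not support them.

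- A reader might infer that the analysis section itself was written for a randomised trial of another size at another site. It states none of these things. The conflict lies in the Study Overview and the Phase 3/Aim 3 text.
- A reader might infer that the BVHC account leaves the comparator undefined, or impossible because every team in the clinic is assigned to the modified model. Sections 2.2 and 5.1 do define eligible concurrent controls: adult BVHC patients with PHQ-9 between 10 and 20, not yet on the modified model, whose providers give usual care. Section 5.1 describes a network of several clinics, so assigning all teams in one clinic need not exhaust the usual-care providers. What is missing is detail: which clinics or teams, what calendar window, and how patients are drawn from those eligible.
- A reader might want a clustered precision loss. It would rest entirely on assumed correlations and an assumed control structure.

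**Conclusion.** The contradiction is real and has to be corrected: as written, the plan gives two allocation methods, two sites, 6 versus 11 clinicians, 30 versus up to 80 patients, and two incompatible routes of patient entry. This rests on direct comparison of current text and needs no assumption. That the Casper text is the older of the two is an inference from its broken sentence and from the agreement of the other sections.

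The half-widths of about 0.72 and 0.44 are illustrative. They assume a 15 + 15 split, d near 0 and no clustering. The main consequence is interpretive: the patient-outcome effect size could be read as randomised when most of the document says it is not. The unnamed usual-care clinics, window and selection rule are a matter for clarification and not a fault of the same weight.

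**What to change.** State one design throughout.

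- Remove the randomisation sentence and the Casper, 6-clinician, 30-patient and 5-per-therapist figures from the Study Overview and the Phase 3/Aim 3 text. Carry the non-randomised BVHC comparison of up to 40 + 40 patients in their place.
- Reconcile section 3.1 (sites), Patient eligibility (contact and consent) and Patient data collection (portal consent and assessments) with sections 4.2, 5.1, 5.2 and 8.2. Editing only the Study Overview and the randomisation sentence would leave these in conflict. For example, the Sheehan Disability Scale is among the portal assessments but not in the patient data listed in 5.2.
- In Data analysis, label the patient-outcome result a non-randomised comparison. Report it with a confidence interval, adjusted for the baseline score already held: the screening PHQ-9 that section 4.6 retains, and the earliest EHR GAD-7 from the historic data in 5.1. The plan defines no baseline date, so say which record counts. State that this adjustment does not remove differences between clinics.

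As a clarification, before data are extracted, name the BVHC clinics or teams that supply usual-care patients, the calendar window, and one selection rule for both groups. Sections 5.1 and 8.2 say some clinics already use the model, so also state whether their patients may count towards the 40 modified-BA patients.

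The cost is wording changes, one adjusted analysis using scores already collected, and possibly a smaller control pool once the clinics and window are fixed.
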